CC2.7 Ensuring that the affiliated sites are using the correct version of the IRB protocol and consent documents and maintaining IRB approval throughout the conduct of the study: Yes

1) If Yes, the mechanism to be employed and 2) if No, indicate who (by role) is responsible:

The Principal Investigator at each site will be responsible for ensuring that the correct versions of the IRB protocol and consent document are being used throughout the study. The site Principal Investigator will also be responsible for maintaining IRB approval by ensuring renewals are submitted in a timely manner. Each site will be required to send the coordinating center a copy of their initially approved protocol and consent document as well as continuing review and modification approvals.

CC2.8 * Data management, including transmission, storage, and analysis: Yes

If Yes, indicate if only de-identified data will be received, describe the process and tools to be used to ensure confidential transmission/storage, and analysis of the data:

The original research files (including the consent forms) will be stored at each of the participating sites. Each site will be responsible for ensuring that their research data/documents are restricted to associated investigators and research staff. Each site will be asked to keep research files under double lock and key and be only accessible to authorized study personnel.

Data will be collected using paper and pencil or using the web-based system Qualtrics. Security measures including log-in procedures for data entry that will be restricted to associated research staff will be implemented. Participant confidentiality will be preserved by linking participant names to numeric IDs at the study sites. This linkage code file will be stored securely at the study sites.

The coordinating center will receive coded data from the participating centers through Qualtrics. We may also receive images and videos of the training tasks from participants through Qualtrics.

CC2.9 * Distributing or storing drugs and/or devices: N/A

1) If Yes, the process for distribution and 2) if No, indicate who (by role) is responsible:

CC2.10 * Indicate other responsibilities not listed above:

The coordinating center will also be responsible for developing the manual of operations for this study.

CC2.11

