
CSIS.O

Indicate the sites where research activities will be performed and/or private information will be obtained.

Choose all sites that apply and/or use Other to include sites not listed:

Sites:

University of Pittsburgh

University of Pittsburgh

Campus:

Main Campus - Pittsburgh

List university owned off-campus research sites if applicable:

ection: Cover Shee

If you selected School, International or Other, list the sites:

*For research being conducted at non Pitt or UPMC sites, upload a site permission letter granting the researcher permission to conduct their research at each external site:

Name Modified Date

CS15.1 Have you, [name], verified that all members of the research team have the appropriate expertise, credentials, and if applicable, hospital privileges to perform those research procedures that are their responsibility as outlined in the IRB protocol?

* Yes

CS15.2 Describe the availability of resources and the adequacy of the facilities to conduct this study:

Adequate staff, time and funds have been allocated to coordinate this multi-site project. The PI, co-investigators and staff working on this project have previous experience coordinating multi-site projects.

!Section: Section 1 - Objective, Aims, Background and Significance!

[reviewer notes-]

1.1 Objective: What is the overall purpose of this research study? (Limit response to 1-2 sentences.)

The objective of the study is to evaluate the effectiveness of remote training to teach clinicians how to train others in wheelchair skills.

1.2 Specific Aims: List the goals of the proposed study (e.g., describe the relevant hypotheses or the specific problems or issues that will be addressed by the study).

Evaluate the ability of remotely trained clinicians (trainers) to teach other individuals (trainees) using the skills and techniques presented in the Wheelchair Skills Training Program (WSTP) by evaluating:

- 1) Wheelchair skills capacity of trainees.
- 2) Wheelchair skills confidence of trainees.

Section: Section 2 - Research Design and Methodology[reviewer notes.]**2.17 What are the main outcome variables that will be evaluated in this study?**

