The main outcome variables are to determine the effectiveness of remote wheelchair skills training include the Wheelchair Skills Test Questionnaire questions on capacity (WST-Q capacity) and confidence (WST-Q confidence), knowledge questions about wheelchair skills (WST knowledge), and remote evaluation through video analysis by the study team on capacity to perform skills. Additionally, we will gather feedback on how the training process could be improved.

2.18 Describe the statistical approaches that will be used to analyze the study data.

* Addressed below:

We will use a paired t-test to evaluate if there is an improvement in knowledge of skills following the respective training programs through knowledge based questionnaires for the trainees. We will determine if capacity and confidence increases through paired comparisons between baseline and follow-up for the WST-Q total scores. Capacity will also be evaluated based on whether participants are successful in each task as determined by a remote rater; in this success will be determined with at least 75% of participants achieving capacity in each task.

A power analysis was completed based on the published study completed with Occupational Therapy students with a pre-WSTP score of $64.8+/-9.0$ and post-WSTP score of $81.0+/-5.2$. Taking this into consideration, we will need a sample size of 23 individuals for a 95% power to detect a difference in the pre-WSTP and post-WSTP scores. We have estimated a sample size of 24 trainers and 72 trainees to account for participants who do not complete the study.

!Section: Section 5 - Potential Risks and Benefit

[reviewer notes.]

5.2

What steps will be taken in the event that a clinically significant, unexpected disease or condition is identified during the conduct of the study?

Not Applicable

[reviewer notes.]

5.8

Will any individuals other than the investigators/research staff involved in the conduct of this research study and authorized representatives of the University Research Conduct and Compliance Office (RCCO) be permitted access to research data/documents (including medical record information) associated with the conduct of this research study?

Yes

5.8.1

Identify the 'external' persons or entity who may have access to research data/documents and the purpose of this access:

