No subjects will be enrolled under this protocol. If a participant from any of the participating centers withdraws from the study, any information collected prior to the date the subject formally withdrew may continue to be used.

5.17

Following the required data retention period, describe the procedures utilized to protect subject confidentiality. (e.g., destruction of research records; removal of identifiers; destruction of linkage code information; secured long-term retention)

Following the required data retention period, the linkage code information will be destroyed. The coded data collected will be retained for an indefinite period of time and will be stored in a secure manner.

Section: Section 6 - Costs and Payment

Reviewer notes:-)

6.1

Will research subjects or their insurance providers be charged for any of the procedures (e.g., screening procedures, research procedures, follow-up procedures) performed for the purpose of this research study?

*

No

Reviewer notes:-)

6.2

Will subjects be compensated in any way for their participation in this research study?

Yes

6.2.1

Describe the amount of payment or other remuneration offered for complete participation in this research study.

For complete participation, Trainers may receive \$255 or \$345, depending on their participation history.

For complete participation, Trainees will receive \$75.

6.2.2

Describe the amount and term of payment or other remuneration that will be provided for partial completion of this research study.

Participants will be compensated for each portion of the study that they complete.

Trainers will be paid \$30 for completing baseline questionnaires and reviewing online material. They will be paid \$60 for practicing the skills in pairs and sending videos for remote review. Trainers will also receive \$30 for completing the post-training questionnaires and providing feedback on the training program(s). If a participant has completed the above listed activities as part of the study "Remote Training Coordinating Center" (PRO15120300), they will receive \$30 for completing the wheelchair skill modules and the pre-/post-confidence questionnaire.

Trainers will receive \$75 for providing wheelchair skills training to a WSTP Trainee. They may provide training to up to 3 Trainees. For complete participation, they may receive \$255 or \$345, depending on their participation history.

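### Section 2.18 has no trainer term although up to 3 trainees share a trainer; if gains correlate within trainer, standard errors are too small and type I error exceeds its nominal level

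*Combined protocol and SAP*

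**What the plan says.** Section 1.2 sets out to judge remotely trained clinicians by the wheelchair skills capacity and confidence of the people they teach. Section 2.18 gives the analysis. For knowledge: "We will use a paired t-test to evaluate if there is an improvement in knowledge of skills following the respective training programs", applied to the trainees. For the other two outcomes: "We will determine if capacity and confidence increases through paired comparisons between baseline and follow-up for the WST-Q total scores". On numbers it says: "We have estimated a sample size of 24 trainers and 72 trainees to account for participants who do not complete the study". That is 72/24 = 3 trainees per trainer on average, and section 6.2.2 gives the maximum for a trainer: "They may provide training to up to 3 Trainees".

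The documents contain no trainer effect, intra-trainer correlation, design effect, robust standard error or trainer-level summary. On data flow, CC2.8 says "The coordinating center will receive coded data from the participating centers through Qualtrics", but not that a trainee's record identifies the trainer. The manual of operations mentioned in CC2.10 is not among the documents.

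**The concern.** A paired t-test assumes that the individual changes are independent of one another. Here trainees come in groups taught by the same person, and the study exists to see how well that person teaches. Some positive correlation of gains within trainer is therefore likely. The mean trainee gain remains a legitimate target and its estimate is not biased by this; its variance is what the plan gets wrong. An understated variance gives p-values that are too small, and any confidence interval from the same analysis is too narrow. The analysis would also leave unreported how much results vary between trainers, which bears directly on the study objective.

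**Working it through.** **Inputs from the documents.** 24 trainers, 72 trainees, up to 3 each (2.18, 6.2.2). Pre score 64.8 (SD 9.0), post score 81.0 (SD 5.2), so the assumed gain is 16.2 points (2.18).

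**Assumptions (not in the documents).** ICC of gains 0.01 to 0.30; two-sided 5% test; pre-post correlation r of 0 or 0.5.

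**SD of change.** sqrt(9.0² + 5.2² − 2·r·9.0·5.2) = 10.39 at r = 0 and 7.83 at r = 0.5.

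**The plan's own figure.** Section 2.18 states 23 individuals for 95% power. An exact paired t calculation on its inputs gives 8 at r = 0, 6 at r = 0.5 and 13 at the extreme r = −1. The 23 is not reproduced, but it errs on the large side and does not affect this point.

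**Design effect.** With equal groups of m, DE = 1 + (m − 1)·ICC, so for m = 3, DE = 1 + 2·ICC. For a smaller layout (8 trainers each with 1, 2 and 3 trainees, n = 48), the sum of squared group sizes is 8·(1 + 4 + 9) = 112 and DE = 1 + (112/48 − 1)·ICC.

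**Type I error.** Approximately 2·(1 − Φ(1.96/√DE)), checked with 200,000 simulated null trials per cell using a one-sample t-test on individual gains. At ICC 0 the simulation returns 5.0% in both layouts.

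**Half-width of the 95% interval.** Unadjusted: t(71)·10.39/√72 = 2.44 points. Adjusted: t(23)·10.39·√(DE/72).

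| ICC | DE, 24×3 | Effective n (of 72) | Type I, formula | Type I, simulated 24×3 | Type I, simulated, average 2 | Adjusted half-width, 24×3 |
|---|---|---|---|---|---|---|
| 0.01 | 1.02 | 70.6 | 5.2% | 5.2% | 5.2% | 2.56 |
| 0.05 | 1.10 | 65.5 | 6.2% | 6.2% | 5.7% | 2.66 |
| 0.10 | 1.20 | 60.0 | 7.4% | 7.3% | 6.5% | 2.78 |
| 0.20 | 1.40 | 51.4 | 9.8% | 9.7% | 8.2% | 3.00 |
| 0.30 | 1.60 | 45.0 | 12.1% | 12.1% | 9.7% | 3.21 |

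In the smaller layout, effective n falls from 48 to between 47 and 34. At SD 7.83 the half-width goes from 1.8 to between 1.9 and 2.4 points.

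Not all of the widening is clustering. Moving from 71 to 23 degrees of freedom alone takes 2.44 to 2.53 at ICC 0. With df held at 71, clustering takes 2.44 to 2.44·√1.02 = 2.46 at ICC 0.01 and to 2.44·√1.60 = 3.09 at ICC 0.30.

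**Effect on the planned result.** For a 16.2-point gain at SD 10.39, t = 16.2/(10.39/√72) = 13.2 unadjusted, and 13.2/√1.60 = 10.5 at ICC 0.30. At this SD the verdict differs only for observed gains between 2.44 points and the adjusted half-width (2.56 to 3.21), that is from 0.23 to at most 0.31 SD of change.

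**Do the remedies work?** A t-test on the 24 trainer means (df 23) gives 4.9% to 5.1% in both layouts. A random-intercept model with df 23, used as a stand-in for Satterthwaite or Kenward-Roger (6,000 trials per cell, ICC 0.05, 0.10 and 0.30), gives 4.0% to 4.7% with 24×3 and 4.3% to 5.3% with an average of 2.

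**The case against.** The strongest reply is that type I error is the wrong headline. If training does nothing, trainers' teaching adds no variance to gains and the paired test is about nominal. Inflation needs a mean gain of zero while trainers truly differ. At ICC 0.30 and SD 10.39 the between-trainer SD is √0.30·10.39 = 5.7 points, so half the trainers would on average be lowering scores. This stands as a caution about the upper figures, although a shared setting or shared assessment could leave some correlation under the null. It does not remove the problem. If the true mean gain shifts all gains equally, the same percentages are the non-coverage of the nominal 95% interval at any true gain, so coverage runs from 94.8% down to 87.9%.

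Other points also have weight:

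- No result near the planned 16.2 points changes. That figure comes from a published study of occupational therapy students, and the plan gives no effect size for confidence or knowledge, so a large gain cannot be presumed there, nor a small one.
- Three trainees per trainer is a ceiling, and 72 already allows for non-completers. The average-2 column covers that case.
- Only the knowledge analysis is explicitly an individual-level t-test. For WST-Q the method is unspecified, and a clustered method could be intended. But 2.18 is where the analysis is stated, and it does not say so.
- The remedies assume independent trainers. Section 6.2.2 describes "practicing the skills in pairs and sending videos for remote review", and CC4.0 lists four sites. An added pair variance share of 0.05 (trainer share 0.10 or 0.20) puts the trainer-mean test at 6.1% to 6.3%, against 10.3% to 12.8% for the individual test. An added site share of 0.02 (trainer share 0.10) puts it at 7.8% against 11.3%. The remedy is imperfect but better in each like-for-like comparison.

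**Conclusion.** The concern holds, conditional on a positive within-trainer correlation of gains. The nesting and the absence of any trainer adjustment are plain from the documents, and the direction of the error follows. Its size rests on assumed values of ICC and alpha: negligible near ICC 0.01, and about double the nominal level or slightly more at ICC 0.30. Power at the planned gain is not threatened. What is at stake is honest precision for all three trainee outcomes, and the error rate for gains near the significance threshold. This should be fixed; it does not undermine the study.

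**What to change.** Add to section 2.18:

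> Change from baseline to follow-up in WST-Q capacity, WST-Q confidence and WST knowledge among trainees will each be analysed with a linear mixed model with a random intercept for trainer and Kenward-Roger or Satterthwaite degrees of freedom. The mean change with its 95% confidence interval and the between-trainer SD will be reported.

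A one-sample t-test on trainer-mean gains is a valid, simpler alternative. It matches the mixed model exactly only when all trainers have the same number of trainees; otherwise it gives each trainer equal weight. Either way, state alpha and sidedness.

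Make sure every coded trainee record carries the trainer's code. Because trainers may also be correlated within practice pairs and sites, describe gains by site. If the pairs are recorded, repeat the test on pair means as a sensitivity check; it holds 5.0% to 5.1% in the pair scenario above.

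The cost is a text change, possibly one added field on the trainee data form, and somewhat wider intervals. Power for the trainer-mean test at the plan's own effect stays at or above 99.9%, even with ICC 1 and r = −1.

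### The paired analyses use only trainees with both scores although non-completion is expected, so the estimated gain is biased if non-completion depends on baseline score or on lack of progress

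*Combined protocol and SAP*

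**What the plan says.** Section 2.18 names two kinds of analysis for trainees' scores. For knowledge: "We will use a paired t-test to evaluate if there is an improvement in knowledge of skills". For WST-Q capacity and confidence: "paired comparisons between baseline and follow-up for the WST-Q total scores". The type of paired comparison for the WST-Q is not specified.

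The sample-size paragraph of the same section says "we will need a sample size of 23 individuals for a 95% power to detect a difference" and then sets the numbers at "24 trainers and 72 trainees to account for participants who do not complete the study". It gives no expected rate of non-completion.

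Section 5.16 says of anyone who withdraws that "any information collected prior to the date the subject formally withdrew may continue to be used". It permits such use but does not say how a baseline score without a follow-up score would enter the analysis.

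The plan states no analysis set, no method for missing follow-up, no sensitivity analysis and no comparison of completers with non-completers. It does not use the term completers-only; that restriction follows from the choice of a paired test.

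**The concern.** A paired difference needs two scores, so the planned analyses estimate the gain among those who finished. The aim in section 1.2 is broader: how well remotely trained clinicians teach trainees. The two agree only if those who leave would have gained as much, on average, as those who stay.

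Enrolling more people keeps the number of pairs up but does not change who is in them. The documents describe no comparison arm in which similar losses might partly cancel, so selective loss goes straight into the headline estimate. At stake is the size of the reported gain, more than whether there is one.

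**Working it through.** **Inputs.** From section 2.18: pre score 64.8 (SD 9.0), post score 81.0 (SD 5.2), so the gain is 81.0 − 64.8 = 16.2; 23 needed for 95% power; 72 trainees. Assumed, because not stated: pre-post correlation r from 0 to 0.8, normal scores, two-sided alpha 0.05, and the rate of non-completion.

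**The plan's own figure.** The SD of the change is √(9.0² + 5.2² − 2r·9.0·5.2): 14.2 at r = −1, 10.39 at r = 0, 7.83 at r = 0.5 and 3.8 at r = 1. A paired t-test with 95% power then needs 13, 8, 6 and 4 pairs. The stated 23 is not reproduced, and power at 23 pairs exceeds 99.9% at every r. The figure errs towards too many participants; that is a separate matter and nothing below rests on it.

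**Does change depend on baseline?** The slope of change on baseline is r·5.2/9.0 − 1 = 0.578r − 1. It is negative for every possible r (−1.58 at r = −1, −0.42 at r = 1). On these SDs, any loss that shifts the baseline mean of completers also shifts their mean gain.

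**Largest bias at 20% non-completion.** Removing exactly the top or bottom fifth of a normal variable moves the mean of the rest by φ(0.842)/0.8 = 0.350 SD. For baseline that is 0.350 × 9.0 = 3.15 points; the bias in the gain is 3.15 × (1 − 0.578r). Removing the fifth with the smallest gains gives 0.350 × SD of change.

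| r | Slope | Highest baselines lost | Lowest baselines lost | Smallest gains lost |
|---|---|---|---|---|
| 0 | −1.00 | +3.2 | −3.2 | +3.6 |
| 0.5 | −0.71 | +2.2 | −2.2 | +2.7 |
| 0.8 | −0.54 | +1.7 | −1.7 | +2.0 |

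Simulation agrees to within about 0.02. These are ceilings at that rate. At 10% loss and r = 0 the baseline ceiling is about 1.8 points, and at 4% about 0.8.

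**Softer link.** If the odds of non-completion double per SD, with 20% lost, simulation over r = 0.7 to 0 gives 0.7 to 1.2 points in either direction for baseline-related loss, and 0.8 to 1.3 upward for loss related to small gains.

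**What a model recovers.** With the top or bottom fifth of baselines lost, a likelihood model using all baselines with an unstructured covariance leaves a bias of about 0. A plain random-intercept model, which forces equal variances at the two times, leaves 0.7 to 1.1 points at r = 0.3 to 0.8. With the smallest gains lost, even the unstructured model stays 0.8 to 1.4 points too high. (The trainer effect was left out of these runs.)

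**Zero change in non-completers.** The all-enrolled gain is 16.2 × share completing: 16.2 × 23/24 = 15.5 at 4.2% loss, × 0.9 = 14.6, × 0.8 = 13.0, × 0.7 = 11.3.

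**Test against zero.** Take r = 0, 30% lost and zero change imputed. The SD is √(0.7 × 108.04 + 0.7 × 0.3 × 16.2²) = √130.7 = 11.4, the SE with 72 trainees is 11.4/√72 = 1.35, and 11.3/1.35 is about 8.4. Complete clustering within trainers of 3 would divide this by √3, leaving about 4.9.

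**The case against.** The best defence is that the plan asks whether scores increase, and selective loss on this scale would hardly change that answer. This stands: the consequence is confined to the size of the gain.

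It is also fair that the SDs come from Occupational Therapy students' WSTP scores and may not fit these trainees, the WST-Q or the knowledge score. If gain were unrelated to baseline, baseline-related loss would cause no bias. The point figures are therefore illustrations. Bias from loss of poor progressers does not need that dependence.

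Two stronger readings are tempting and unsupported.

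- A reader might infer that the bias must run upward because strugglers leave. If strugglers are those who start low, then on these SDs their loss lowers the completer gain, since low starters gain most. Only loss tied to lack of progress itself points upward, and the documents do not say which would dominate.
- A reader might take 23 needed against 72 enrolled as a sign that the plan expects about two thirds to be lost. But 72 is 24 × 3, and section 6.2.2 lets each trainer teach up to 3 trainees. The ratio is not a completion rate, and no rate is given.

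A last objection is that a model adds little with two time points. That is wrong for baseline-related loss if the variances may differ, and partly right for loss driven by lack of progress, which the model does not fully correct.

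**Conclusion.** The concern holds as a limit on the estimate. The planned paired analyses describe completers, and the plan's only answer to non-completion does nothing about selection. On the planning SDs and an assumed 20% loss, the error in a 16.2-point gain is at most about 1.7 to 3.2 points in either direction for baseline-related loss, and about 2.0 to 3.6 points upward for loss of the smallest gains. It is nearer 1 point under a moderate link and smaller at lower loss. These figures rest on an assumed r of 0 to 0.8, normal scores, an assumed loss rate and SDs borrowed from another population. The direction is not established, and the conclusion that scores rise is not threatened. The change is worth making because it is cheap and the gain is the main result.

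**What to change.** In section 2.18:

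1. Define the analysis set as all trainees with a baseline score, and state the expected rate of non-completion.
2. For knowledge, WST-Q capacity and WST-Q confidence, estimate the mean change with a likelihood-based repeated-measures model. Use baseline and follow-up as outcomes, time as a fixed effect, an unstructured covariance (so that the two variances may differ) and a trainer random effect. Report the change with its 95% CI. A plain random-intercept model is not enough.
3. Pre-specify one sensitivity analysis that sets change to zero for trainees without follow-up. It is a deliberately cautious reference for loss driven by lack of progress, which the model does not correct.
4. Keep the paired completer result as secondary, and report completion counts and baseline scores by completion status.

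The cost is a few sentences of SAP text and slightly more analysis work; no new data are needed. The headline gain may come out smaller.

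### Does the 75% video rule in 2.18 pool trainers with trainees and so misjudge trainee capacity?

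*Combined protocol and SAP*

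**What the plan says.** Section 1.2 sets the aim as the ability of remotely trained clinicians to teach others, and its first measure is "Wheelchair skills capacity of trainees". Section 2.17 lists remote video evaluation of capacity among the main outcomes, beside the WST-Q capacity and confidence scores and the knowledge questions.

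Section 2.18 gives the video outcome one rule: "success will be determined with at least 75% of participants achieving capacity in each task", with a remote rater deciding each task. No group is named and no denominator is given. Two other phrases in 2.18 bear on the reading. The knowledge comparison is restricted, through "knowledge based questionnaires for the trainees". The sample-size sentence uses the word *participants* for everyone: "We have estimated a sample size of 24 trainers and 72 trainees to account for participants who do not complete the study".

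Section 6.2.2 pays trainers for "practicing the skills in pairs and sending videos for remote review". A trainer who already did those activities in the earlier remote-training study is paid instead "for completing the wheelchair skill modules and the pre-/post-confidence questionnaire". Sections 5.8.2 and 5.15 make recording and uploading optional.

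**The concern.** Read literally, with *participants* meaning what it means in the sample-size sentence, the rule covers all 96 people in CC1.1. The trainers' own skill would then enter a verdict that should be about trainees. Trained clinicians may well outperform the people they teach, so a task could be declared successful with trainees below 75%.

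The payment text seems to add a second difficulty. Some trainers have no paid video step in this study. If they stayed in the denominator as non-achievers, a task could be declared unsuccessful with trainees well above 75%. Because 2.17 counts video-rated capacity among the main outcomes, either error would give a wrong answer on Aim 1 for that task.

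**Working it through.** **Inputs.** 24 trainers and 72 trainees (2.18); 96 in total (CC1.1); threshold 75% (2.18); payments from 6.2.1 and 6.2.2.

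**The plan's own figures.** 24 + 72 = 96, as CC1.1 states. Trainer payments: 30 + 60 + 30 + 3 × 75 = $345, and 30 + 3 × 75 = $255. Both agree with 6.2.1.

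**Counts if everyone is pooled and rated.** The task passes at 0.75 × 96 = 72 successes, so trainees needed = 72 − (trainers successful). A trainee-only rule needs 0.75 × 72 = 54.

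| Trainers successful (of 24) | Trainees needed (of 72) | Trainee rate |
|---|---|---|
| 24 | 48 | 66.7% |
| 22 | 50 | 69.4% |
| 18 | 54 | 75.0% |
| 13 | 59 | 81.9% |
| 12 | 60 | 83.3% |

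The two rules coincide when 18 of 24 trainers succeed. A task fails at 71 successes or fewer. To fail with 58/72 trainees (80.6%), at most 71 − 58 = 13 trainers (54.2%) may succeed, so the trainers would have to do far worse than the people they taught.

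**Chance of a pass.** These are exact binomial sums with independent ratings. All true rates are assumed for illustration, since the documents give none.

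- Trainees at 70%, all 96 rated: trainee-only 0.21. Pooled 0.25, 0.34, 0.55 and 0.67 with trainers at 75%, 80%, 90% and 95%.
- Trainees at 85%, 12 trainers without a video, the 12 filmed trainers at 95%: trainee-only 0.99. Pooled with the 12 counted as failures (72 of 96 needed): 0.65. Pooled with the 12 left out (0.75 × 84 = 63 needed): 0.999.

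So the false pass is real if the groups are pooled and trainers do better than trainees. The false fail in this example comes entirely from scoring unrated people as failures. Section 2.18 makes success a rater's determination, and someone without a rated video has none.

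**Is pooling what the plan says?** Three readings are open.

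1. *Both groups.* The sample-size sentence uses the word this way, but it is a remark about attrition and not a definition.
2. *Trainees only.* The rule comes after the trainee knowledge test and is introduced as a further look at capacity, the trainee outcome in 1.2.
3. *Trainers only.* Section 6.2.2 uses the word for a trainer alone ("If a participant has completed the above listed activities as part of the study"), and trainers are the only role the supplied text names as sending videos for remote review. The trainee payment detail is not in the supplied text, so its absence shows nothing.

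The 66.7% and above-80% figures arise only under the first reading.

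**Does the payment text conflict with the rule?** No. It shows that trainers on the $255 track are not paid again for a step they completed in the earlier study. It does not show that they lack a rated video, or that earlier ratings are unusable.

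**The case for a change.** The strongest reply is that every reading leaves something unsaid. If the groups are pooled, the verdict can mislead on Aim 1. If the rule is for trainers only, it says nothing about Aim 1. If it is for trainees only, the text should say so and state how people without a video count. A few words would settle this before any rating is seen, so that nobody picks the denominator afterwards, and the price would be small: the standard error at 75% goes from √(0.1875/96) = 4.4 points to √(0.1875/72) = 5.1 points.

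Part of this stands. The population and denominator are undefined, and naming them would have been tidier. But this is missing detail, not a rule that is wrong. The ratings are made person by person and each person's role is known, so trainee and trainer rates can be reported for each task whatever the sentence says, and a reader can compare either with 75%. No test, error rate or sample size depends on the choice.

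A trainee-only rewrite also carries a risk. If the benchmark was meant for trainers, the rewrite would discard it and set a new one on trainee videos that the supplied text does not show to exist. The local-site applications and the manual of operations, which are not supplied, may say who is filmed.

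**Conclusion.** The concern does not call for a change. Section 2.18 leaves the group and the denominator of the 75% rule unstated. Under the pooled reading, with all 96 people rated and all 24 trainers successful, a task could pass with trainees at 66.7%, which is 6 trainees short of the 54 that a trainee-only rule needs. The opposite error needs 13 or fewer successful trainers, or an imputation that the plan does not make. The claimed conflict with the payment schedule is not there.

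This is a gap that analysts fill sensibly: show trainee and trainer rates side by side for each task, with the numbers not rated, and rest any statement on Aim 1 on the trainee rate if trainees are filmed. The benchmark carries no test, and the paired WST-Q and knowledge comparisons stand apart from it. The conclusion assumes that ratings can be separated by role, which follows from their being made for each participant. The pass probabilities rest on assumed rates and independent ratings; the counts do not.
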